## **7.8. Regulatory Reporting Requirements**

The investigator must promptly report all SAEs to the sponsor in accordance with the procedures detailed in Section **7.7**, "Prompt Reporting of Serious Adverse Events to the

Sponsor.” Reporting of SAEs to the Regulatory Authorities will be the responsibility of the Sponsor. Serious Unexpected Suspected Adverse Reactions (SUSARs) will be reported to the Regulatory Authorities. The sponsor has a legal responsibility to notify, as appropriate, both the local regulatory authority and other regulatory agencies about the safety of a product under clinical investigation. Prompt notification of SAEs by the investigator to the appropriate project contact for SAE receipt is essential so that SSARs that are either unexpected or observed with increasing occurrence be reported and legal obligations and ethical responsibilities regarding the safety of other subjects are met.

Investigator letters are prepared according to sponsor policy and are forwarded to the investigators as necessary. An investigator letter is prepared for any SAR that is attributable to study medication, serious, and unexpected. The purpose of the investigator letter is to fulfill specific regulatory and Good Clinical Practice (GCP) requirements regarding the product under investigation.

The investigator, or responsible person according to local requirements, must comply with requirements related to the reporting of SAEs to the IRB or IEC. It will be Investigator/CRO responsibility to report the SAE to all the participating Investigators during the study.

### **7.9. Precautions**

If a female subject becomes pregnant during the study, study product must be discontinued immediately, the subject should immediately be withdrawn from the study and early termination study procedures must be performed. The subject must be followed through the pregnancy and delivery and up to 4 weeks after delivery for infant status.

Pregnancy occurring during a clinical investigation, although not considered a SAE, must be reported by the Investigator to Sponsor within the same timelines as a SAE (within 24 hours). The Investigator should report the event to the Sponsor immediately and complete the Pregnancy Report Form (see Section [7.7](#) for contact information).

The expected date of delivery or expected date of the end of the pregnancy should be included in this information. The Investigator is instructed to contact the subject every 3 months until the end of her pregnancy and report the outcome to the sponsor. The Investigator is instructed to contact the subject for 4 weeks after delivery for follow up on infant status.

Details of the pregnancy, delivery and health of the infant should be recorded on the Pregnancy Report Form.

The following outcomes of pregnancy fall under the criteria for serious adverse events and should be reported as such: delivery complications, spontaneous abortion, stillbirth, death of newborn baby, congenital anomaly, and anomaly in a miscarried/stillborn fetus.

## 8. STATISTICAL METHODOLOGY

### 8.1. Determination of Sample Size

The sample size of 120 subjects for this study was selected empirically without a formal statistical assumption. However, group sizes of 30-40 per group are typically sensitive in the dental pain model to detect acute drug effects.

### 8.2. Study Endpoints

#### 8.2.1. Efficacy Endpoints

The primary efficacy endpoint will be the summed pain intensity difference over the first 6 hours (SPID6) between DFN-15 doses and placebo. The comparison of primary interest is DFN-15 doses vs. placebo.

Key secondary efficacy variables will include the following:

- Total Pain Relief (TOTPAR) over 2, 4, 6 and 8 hours using a 5-point categorical scale (TOTPAR2, TOTPAR4, TOTPAR6 and TOTPAR8)
- Summed Pain Intensity Differences (SPID) at 2, 4 and 8 hours post-dose (SPID2, SPID4 and SPID8)
- Time to perceptible and meaningful pain relief as measured by two stopwatch technique
- Proportion of subjects reporting treatment satisfaction outcome as either 2 = good, 3 = very good or 4 = excellent, on the 5-point categorical scale
- Time to use of rescue medication and percentage of patients using rescue medication
- Pain intensity difference at each NPRS time point (15, 30, and 45 min and 1, 1.5, 2, 3, 4, 5, 6, 7, and 8 h)
- Pain relief at each time point (15, 30, and 45 min and 1, 1.5, 2, 3, 4, 5, 6, 7, and 8 h)
- Characterization of plasma pharmacokinetic profiles of DFN-15 doses in fasting conditions (using  $C_{max}$   $AUC_{0-t}$ ,  $T_{max}$ ; Other pharmacokinetic parameters like  $AUC_{0-0.25}$ ,  $AUC_{0-0.5}$ ,  $AUC_{0-0.75}$ ,  $AUC_{0-1}$ ,  $AUC_{0-2}$ ,  $AUC_{0-3}$ ,  $AUC_{0-4}$ ,  $AUC_{0-6}$  will also be calculated)

Additional exploratory analysis will be performed and pre-specified in the Statistical Analysis Plan (SAP).

The comparison of primary interest in the study is DFN-15 250 mg dose versus placebo. The other comparisons include DFN-15 125 mg versus placebo, DFN-15 62.5 mg versus placebo and between two DFN-15 dose levels.

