### **3. INVESTIGATIONAL PLAN**

#### **3.1. Overall Study Design**

This is a Phase 2, randomized, double-blind, parallel group, dose-ranging placebo-controlled evaluation of the analgesic efficacy, safety, tolerability and pharmacokinetics of DFN-15 in adult subjects who experience post-operative pain after undergoing bilateral third mandibular molar extraction. The study will randomize approximately 120 subjects across 1-3 sites.

Subjects will be at least 18 years to 60 years of age and will be scheduled to undergo elective bilateral mandibular third molar extraction under local anesthesia. The mandibular third molars must involve a full or partial bony impaction confirmed by radiographic evidence (panoramic x-ray).

After signing the informed consent: demographics, medical/medicinal history, physical examination (including height, weight and BMI), dental examination, baseline clinical laboratory testing, 12-lead electrocardiogram (ECG), vital sign measurements, urine pregnancy testing (females of child bearing potential) and urine drug and alcohol screen will be completed during the screening visit.

On the day of surgery (Day 1), prior to surgery, eligibility will be confirmed through updating medical/medicinal history, 12-lead electrocardiogram (ECG), vital sign measurements, urine pregnancy testing (females of child bearing potential), urine drug and alcohol screen, and review of inclusion exclusion criteria. A patient training program will be implemented to ensure that all subjects understand the relevant scales and assessments prior to study participation. Eligible subjects will undergo bilateral mandibular third molar extractions. Subjects who experience acute postoperative pain of ‘moderate’ to ‘severe’ intensity, on a 4-point categorical pain intensity scale (0= none, 1= mild, 2= moderate, 3= severe), within 6 hours following the end of surgery, and a pain intensity  $\geq 5$  on an 11-point numeric pain rating scale (NPRS), will be eligible for randomization and will stay at the study center for at least approximately 8 hours after treatment initiation.

Subjects who meet all of the inclusion and none of the exclusion criteria in the protocol will be randomized in a 1:1:1:1 ratio to receive a single oral dose of DFN-15 62.5 mg, DFN-15 125 mg, DFN-15 250 mg or placebo. The time of the study drug administration will be designated as T0.

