### **8.3. General Considerations for Statistical Analysis**

#### **8.3.1. Analysis Datasets**

Modified Intent-to-Treat (mITT) Analysis Set: The mITT set will include all subjects who receive study drug, and have recorded at least one post dosing efficacy score.

Safety Set: The safety set will include all treated subjects and will be used for safety and tolerability assessments.

Pharmacokinetic Set: The pharmacokinetic set will include all subjects who have received a dose of DFN-15 and have at least one quantifiable concentration of celecoxib in plasma.

Non-compartmental analysis as specified in a PK Analysis Plan will be used to estimate pharmacokinetic parameters and to present descriptive statistics using the Pharmacokinetic Set. Additional exposure-response analysis may be built in the full statistical analysis plan (SAP). Comparisons will be performed at the 0.05 two-sided significance level unless otherwise specified. No adjustments for multiplicity will be performed. Additional details of the analysis will be provided in the SAP and/or the clinical study report. The SAP will supersede the protocol in case of a discrepancy.

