8.2.2 Summed Pain Intensity Difference

The primary efficacy endpoint is the summed pain intensity difference over the first 6 hours (SPID₆) between each of the DFN-15 dose levels and placebo. SPID₆ is created by summing the time weighted pain intensity differences (PID) scores using the area under the PID curve methodology.

All SPID calculations will be done using the standard trapezoidal rule:

SPIDx =

$$\sum_{i=0}^{x} \left(\frac{PID_i + PID_{i+1}}{2} \right) * (T_{i+1} - T_i)$$

Where: $PID_i = P_i - PIBL$ (Pain Intensity score at time i and Pain Intensity score at Baseline), $(T_{i+1} - T_i)$ is the Time difference in minutes between time i and time i+1, and $(T_{i+1} - T_i)$ is the Time difference in minutes between time i and time i+1.

Baseline PI will be defined as the last PI recorded prior to first dose. Time points will be selected for inclusion into specific SPID periods based on nominal time points (e.g., all scheduled assessments from Baseline to the Hour 6 assessment will be included in SPID₆).

Except for baseline, the actual date/times of assessments will be used in the SPID calculation whenever collected. For baseline, rather than the actual time recorded, baseline pain will be considered to be recorded at time 0(i.e., time of first dose).

All imputation, as described in Section 8.1.1, will be performed prior to the SPID calculations.

The individual SPID variables will also be presented in subject listings.

The secondary efficacy SPID outcomes (SPID₂, SPID₄, and SPID₈) are calculated similarly to SPID6 adjusting for the respective time periods.

All SPID endpoints will be analyzed using an ANCOVA with treatment as the main effect and both baseline pain intensity and BMI as covariates. Mean SPID values over time will be displayed graphically.

The results of the ANCOVA will be presented in summary tables with standard summary statistics as well as least square (LS) means, active dose level vs. placebo LS mean differences

(treated group – placebo), standard errors, confidence intervals (CI) and paired-comparison p-values with Dunnett's test.

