8.2.3 Proportion of Responders

NPRS responders are defined as subjects who achieve \geq 30% (called 30% Responders) or \geq 50% (called 50% Responders) improvement in PI NPRS over the baseline value recorded at T0 at any time prior to first use rescue and up to 8 hours. All imputation as described in Section 8.1.1 will be performed prior to percent improvement and responder calculations. If any scheduled post-baseline NPRS score prior to rescue medication (if rescue was taken) meets or exceeds the threshold, regardless of if the subject subsequently loses their response, then the subject will be counted as an overall responder. Otherwise, the subject will be considered a non-responder. In addition, the proportion of subjects who achieve a 30%/50% improvement from baseline will also be calculated at each time point and displayed graphically.

Percent improvement = (baseline value - post-baseline value) × 100 / (baseline value)

The proportion of subjects experiencing \geq 30% and \geq 50% improvement in NPRS (responders) will be analyzed using chi square (CMH) test or, alternatively, a Fishers exact test if there are less than 5 subjects in any category. The testing of each dose level of DFN-15 vs. placebo will be performed separately.

Summary tables will present the by-treatment group descriptive statistics of proportions with active vs. placebo odds ratios, 95% confidence intervals and CMH chi-square or Fisher exact p-values. A cumulative proportion of responders figure will also be presented.

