8.3 General Analysis Methods

SPID and TOPAR endpoints will use Dunnett's test to account for multiplicity within each of those endpoints. All other *p*-values are presented without adjustment for multiplicity. The mITT population will be primary population used for all efficacy analyses. The PP population will be used as a supplemental analysis for SPID, TOTPAR, PID by timepoint, PR by timepoint, and peak pain relief.

In all cases, the null hypothesis being tested is that the means of the two treatment groups are equal, and the alternative is that the means are not equal:

- H₀: there is no treatment difference
- H_A: there is a treatment difference

If more than 1 center is used, then center effect will be added to the SPID6 ANCOVA model to investigate the impact. If the center effect is significant at the 0.05 level, then center will be added to the log-rank test for time to meaningful and perceptible pain relief analyses. Additionally, treatment-center interactions will be tested in the ANCOVA analysis of the SPID6 endpoint. If this interaction is significant at the 0.10 level, then the interaction term will be included in a sensitivity analysis.

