11.0 Other Analyses

Any additional analyses conducted will be considered exploratory and identified as post hoc in the CSR.

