13.0 Changes to the Analyses Planned in the Protocol

Any deviations from the statistical plan will be described and a justification given in the CSR.

Statistical Analysis Plan Version: 2.0

Effective Date: 08OCT2018

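### The protocol of this dose-ranging trial lists comparisons between DFN-15 dose levels; the SAP names only contrasts with placebo and does not record the omission.

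*Protocol*

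**What the plan says.** Protocol 3.1 describes the study as a "dose-ranging placebo-controlled evaluation of the analgesic efficacy" and of safety, tolerability and pharmacokinetics. Protocol 8.2.1 makes the comparison with placebo the primary interest and then adds: "The other comparisons include DFN-15 125 mg versus placebo, DFN-15 62.5 mg versus placebo and between two DFN-15 dose levels". The analysis sections that follow (Protocol 8.5.1 and 8.5.2) specify only Dunnett's test of each dose against placebo.

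The SAP's contrasts are these:

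- SPID (8.2.2) and TOTPAR (8.2.5): "active dose level vs. placebo LS mean differences", with standard errors, CIs and Dunnett p-values. SAP 8.3 confirms: "SPID and TOPAR endpoints will use Dunnett's test to account for multiplicity within each of those endpoints".
- PID by timepoint (8.2.1): each dose against placebo, plus all DFN-15 arms pooled against placebo.
- Responders (8.2.3): "The testing of each dose level of DFN-15 vs. placebo will be performed separately".
- Time to peak relief, stopwatch times and time to rescue (8.2.7, 8.2.9, 8.2.10): log-rank tests of each dose against placebo.
- Proportion satisfied and proportion rescued (8.2.8, 8.2.11): active against placebo. The ANCOVA of satisfaction as a continuous score names no contrast.

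The table list in SAP 15.1 has no between-dose or trend output. SAP 13.0 lists no departures from the protocol; it says only: "Any deviations from the statistical plan will be described and a justification given in the CSR". The document history in SAP 16.0 does not mention the omission. On exposure-response, Protocol 8.3.1 is permissive: "Additional exposure-response analysis may be built in the full statistical analysis plan (SAP"). The SAP contains none, and Protocol 8.7 sends PK-PD work to a separate plan.

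**The concern.** A dose-ranging trial is read for how its doses differ. If the SAP is followed as written, the report will carry three separate verdicts against placebo and no interval for any difference between doses. The natural shortcut is to treat a dose that is significant as better than one that is not. At 30 per arm that inference is unreliable, because doses with identical true effects often land on opposite sides of the threshold.

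There is also a question of status. SAP 11.0 says: "Any additional analyses conducted will be considered exploratory and identified as post hoc in the CSR". A comparison that the protocol lists could therefore reach the report labelled post hoc only because the SAP did not carry it over.

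**Working it through.** **Inputs from the documents.** 120 subjects randomised 1:1:1:1, so 120/4 = 30 per arm. Two-sided α = 0.05 (SAP 3.0). ANCOVA with treatment, baseline pain intensity and BMI (SAP 8.2.2). The documents give no effect size, SD or power, so there is no stated figure to reproduce.

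**Assumptions.** Effects are in units of the residual SD, over a range. All 120 subjects are analysed.

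**Precision of a two-arm difference.**

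- Residual df = 120 − 4 − 2 = 114.
- SE of any difference between two arms = √(2/30) = 0.258 SD.
- Unadjusted t critical value 1.981: 95% CI half-width = 1.981 × 0.258 = 0.51 SD.
- Tukey critical value for the three dose pairs 2.375: half-width = 2.375 × 0.258 = 0.61 SD.
- Dunnett two-sided critical value for three doses against placebo: 2.381.

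**How often the verdicts split when the doses are equal.** I simulated 1,000,000 trials per scenario, giving all three doses the same true effect. A dose counts as significant if t > 2.381 in its favour. A split means that at least one dose is significant and at least one is not, so P(split) = P(any significant) − P(all three significant).

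| True effect, all doses (SD) | Power per dose | Any significant | All three | Split |
|---|---|---|---|---|
| 0.5 | 33% | 56.7% | 12.3% | 44% |
| 0.6 | 48% | 72.7% | 23.5% | 49% |
| 0.8 | 76% | 93.1% | 55.8% | 37% |
| 1.0 | 93% | 99.1% | 84.2% | 15% |
| 1.2 | 99% | 99.9% | 96.8% | 3% |

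**The opposite error.** With true effects of 0.8, 1.0 and 1.2 SD, all three doses are significant in 73% of trials although the doses differ.

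**What a direct between-dose contrast can do.** Power of the unadjusted comparison of two doses comes from the noncentral t with noncentrality δ/0.258:

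- δ = 0.4 SD: 34%
- δ = 0.6 SD: 63%
- δ = 0.8 SD: 87%

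**False differences from three unadjusted CIs.** With three equal doses, at least one of the three intervals excludes zero in about 12% of trials. Among the split trials the share is 20% to 28% for effects of 0.5 to 1.0 SD.

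**The case against.** The case against is substantial, and much of it stands.

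- **The comparison is marginal in the protocol.** The stated efficacy objectives are dose against placebo, and the between-dose item comes last in a list without pair, endpoint or method. The protocol's own analysis sections do not implement it, so the mismatch begins there. This stands. It makes the matter one of completing and reconciling the plan, and it rules out the reading that a fully specified analysis was lost.
- **The SAP supersedes the protocol.** That settles which text governs where the two differ. It does not show that the omission was intended, because the SAP is silent and gives no reason.
- **Readers can work it out.** Subtracting two LS means and applying roughly the printed standard error comes close to the missing interval. This stands too, so it would be wrong to say that the outputs leave the reader with nothing. An interval that readers must build for themselves is still not a planned result.
- **Prespecification remains open.** One might infer from SAP 11.0 that any between-dose analysis must now be post hoc. SAP 8.4 does not support that: exploratory analyses can be documented in a later SAP version.
- **Dose-effect evidence may come from elsewhere.** One might infer that the trial has no plan to relate dose to effect. The documents do not support that, because PK-PD analysis belongs to a separate plan that was not supplied. The point is therefore limited to the SAP.
- **The split rates depend on assumed effects.** They do. Dunnett power of 80% per dose needs about 0.83 SD. Beyond that, splits become less frequent and are rare by 1.2 SD. Equal effects over a fourfold dose range are also an assumption.

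**Conclusion.** The gap between Protocol 8.2.1 and the SAP is real: a listed comparison has no planned estimate or CI and no recorded withdrawal. Using significance against placebo as a proxy for dose differences would mislead in a sizeable share of trials if effects are moderate (37% to 49% splits at 0.5 to 0.8 SD with equal doses), and seldom if they are large (3% at 1.2 SD). These rates rest on 30 analysed per arm, the ANCOVA as specified and assumed effects.

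A reader might infer that the primary analysis or its error control is compromised. It is not: Dunnett's test answers the dose-placebo question that the plan puts first, and nothing here disputes it. This is a cheap improvement to a Phase 2 plan.

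**What to change.** Before unblinding, do one of the following.

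1. Add to SAP 8.2.2 and Table 14.2.1.1, from the same SPID6 ANCOVA, the LS mean difference for 250 minus 62.5 mg, and preferably also 125 minus 62.5 and 250 minus 125 mg, each with a 95% CI. Label them supportive and outside the Dunnett family. Either say that they are unadjusted or use Tukey intervals. State that dose differences will be described from these intervals, not from which Dunnett p-values are below 0.05, and that an interval including zero does not show the doses to be equal. A slope per doubling of dose is not needed: with 62.5, 125 and 250 mg equally spaced on the log scale, it is half of the 250 minus 62.5 mg difference.
2. Record in SAP 13.0 that the between-dose comparison is withdrawn, with the reason.

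Leave Dunnett's test for dose against placebo unchanged in either case.

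The cost is a few contrast statements and table rows from a model already fitted, with no new data and no change to conduct. Two downsides should be stated in the report: the intervals will often be inconclusive, and three unadjusted intervals carry the roughly 12% chance of a false difference shown above. Tukey intervals control the second at the price of a wider half-width, 0.61 instead of 0.51 SD.

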#### 8.2.2. Pharmacokinetic Endpoints

Key pharmacokinetic endpoints will be  $C_{max}$ ,  $AUC_{0-t}$  and  $T_{max}$ . Other pharmacokinetic parameters like  $AUC_{0-0.25}$ ,  $AUC_{0-0.5}$ ,  $AUC_{0-0.75}$ ,  $AUC_{0-1}$ ,  $AUC_{0-2}$ ,  $AUC_{0-3}$ ,  $AUC_{0-4}$ ,  $AUC_{0-6}$  will also be calculated. Any other additional parameters requiring estimation will be included in the PK Analysis Plan.

### **8.2.3. Safety Endpoints**

The safety endpoints will include the following:

- 1) incidence of AE's and SAEs
- 2) incidence of abnormal clinical laboratory tests, including routine blood chemistry and hematology, coagulation parameters and urinalysis
- 3) incidence of clinically significant changes in vital signs parameters
- 4) incidence of clinically significant abnormal ECG findings

### **8.3. General Considerations for Statistical Analysis**

#### **8.3.1. Analysis Datasets**

Modified Intent-to-Treat (mITT) Analysis Set: The mITT set will include all subjects who receive study drug, and have recorded at least one post dosing efficacy score.

Safety Set: The safety set will include all treated subjects and will be used for safety and tolerability assessments.

Pharmacokinetic Set: The pharmacokinetic set will include all subjects who have received a dose of DFN-15 and have at least one quantifiable concentration of celecoxib in plasma.

Non-compartmental analysis as specified in a PK Analysis Plan will be used to estimate pharmacokinetic parameters and to present descriptive statistics using the Pharmacokinetic Set. Additional exposure-response analysis may be built in the full statistical analysis plan (SAP). Comparisons will be performed at the 0.05 two-sided significance level unless otherwise specified. No adjustments for multiplicity will be performed. Additional details of the analysis will be provided in the SAP and/or the clinical study report. The SAP will supersede the protocol in case of a discrepancy.

